Dose-proportional increases in systemic exposure based on AUC and C_{max} were observed over the single dose range of [redacted] to [redacted]. Following multiple doses at [redacted], [redacted], [redacted], and [redacted] MT-7117 was rapidly absorbed with median t_{max} values ranging from 4 to 5 hours post-dose on both Day 1 and Day 14. Mean $t_{1/2}$ values ranged from 6.28 to 15.55 hours on Day 1 and 10.56 to 18.97 hours on Day 14. Systemic exposure to MT-7117 in plasma, based on calculation of AUC and C_{max} , appeared to increase in a slightly more than dose-proportional manner over the [redacted] to [redacted] dose range. Steady-state was generally reached by 5 days of multiple dosing.

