2.2.4 Safety Assessments

- Treatment-emergent adverse events (AEs) (including serious adverse events [SAEs] and adverse events of special interest [AESIs]).
- Physical examination.
- Vital signs (blood pressure, pulse rate, and body temperature).

Mitsubishi Tanabe Pharma Development America, Inc.

- Clinical laboratory examinations (hematology, coagulation, biochemistry, and urinalysis), including liver function markers (ALT, AST, GGT, ALP, direct and total bilirubin).
- 12-lead ECG at Baseline and EOT.
- Nevi appearance (assessed by a dermatologist or other qualified site staff). Any nevi undergoing change of clinical concern during active treatment will be biopsied for follow up.

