4.5 Withdrawal of Individual Subjects

A subject will be withdrawn from study if ANY of the following criteria are met:

1. The subject requests to voluntarily withdraw from further participation in study.
2. The subject is significantly noncompliant with the protocol.
3. Continuing in the study would be detrimental to the subject's safety in the opinion of the Investigator, e.g.,
 - a. The subject experiences intolerable AEs or SAEs.
 - b. The subject has clinically significant changes in safety parameters at any of the post-dose time points, as confirmed with a repeat assessment performed as soon as possible after the initial out-of-range result.
 - c. If there are any clinically significant adverse findings from post-baseline nevi evaluation, subjects will not be allowed to continue taking study medication (see Section 6.9.4). If biopsy findings are benign, subject may reinitiate study treatment based on investigators discretion.
 - d. Development of any clinically significant liver dysfunction, as follows:
 - i. ALT or AST $>6 \times$ ULN.
 - ii. ALT or AST $>4 \times$ ULN for more than 2 weeks.
 - a) Elevated total bilirubin $>2 \times$ ULN and ALT or AST $>2 \times$ ULN or
 - b) Symptoms consistent with liver dysfunction (e.g., fatigue, nausea, vomiting, abdominal pain or tenderness, fever, rash, eosinophilia $>5\%$) with concomitant ALT or AST values $>3 \times$ ULN.

Subjects (meeting above criteria) do not require withdrawal if alternative etiology is identified on discussion with the Study Medical Monitor.

Subjects meeting above criteria (with or without alternative etiology) should be reported as hepatic AE of special interest (AESI) (see Section 8.3).

These subjects will be discontinued from treatment but may be managed on study per the Investigator's discretion and followed per protocol (see Section 8.6). In addition, a subject may be withdrawn from treatment at any time for reason(s) other than those listed here.

If a subject is discontinued prematurely from the treatment or the study, the date the subject is withdrawn and the reason for withdrawal will be recorded on the site source documents and in the electronic Case Report Form (eCRF). Subjects who withdraw or are withdrawn from study treatment should be encouraged to complete all study visits and study procedures as outlined in the protocol.

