In case of permanent discontinuation from study, the end of treatment and follow-up visit assessments should be performed, as completely as possible (Sections 5.3.2.7 and 5.3.3, respectively). Unresolved AEs and SAEs will be followed up on according to Section 8.10.

For discontinued subjects who will not revisit the clinic, the site will perform scheduled phone calls for the collection and source documentation for safety information (AEs, concomitant medication, and date of last dose of medication). Return of unused medication and any other materials (e.g., diary) will be performed by courier where allowed.

In the event that a subject elects not to return to the study site for the end of treatment or Follow-up visit, the Investigator must make every effort to contact the subject to review/capture all AEs, assess dosing compliance, review concomitant medication and make every effort to complete all end of study assessments.

Subjects withdrawn from the study following randomization onto double-blind treatment may not re-enter the study. Subjects withdrawn from treatment may remain on study and continue with study procedures off treatment based on the Investigators clinical discretion.

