5.3.2.6 Visit 7 (Week 12, Day 85±7)

The following assessments will be performed (please refer to Table 5.1-1 for details regarding the complete time and events schedule for this study):

- Abbreviated physical examination (including body weight).
- Vital signs (including sitting blood pressure, pulse rate, and oral body temperature).
- Routine laboratory evaluations (hematology; biochemistry; coagulation; urinalysis).
- Urine pregnancy test (for female subjects of child-bearing potential only).
- Blood sampling for PK analysis.
- Dispensing of MT-7117 or placebo.
- Medication accountability.
- Review sunlight exposure diary (re-educate subject if necessary).
- AE and concomitant medication recording.

5.3.2.7 Visit 8: End of Treatment Visit (Week 16, Day 113±7 or Early Termination)

Subjects will attend the end of treatment visit at Week 16 or early termination. The following assessments will be performed (please refer to Table 5.1-1 for details regarding the complete time and events schedule for this study):

- Abbreviated physical examination (including body weight).
- 12-lead ECG.
- Vital signs (including sitting blood pressure, pulse rate, and oral body temperature).
- Routine laboratory evaluations (hematology; biochemistry; coagulation; urinalysis).
- Plasma porphyrin and erythrocyte protoporphyrin sample collection.
- Urine pregnancy test (for female subjects of child-bearing potential only).

- Blood sampling for PK analysis (at the visit and 3 to 4 hours after the first PK sample collection [both post-dose]).
- Medication accountability.
- Subject Questionnaire for study medication.
- PROMIS-57 questionnaire.
- PGIC.
- Review sunlight exposure diary (re-educate subject if necessary).
- Melanin density evaluation as measured by spectrophotometer.
- Nevi evaluation and biopsy (for any nevi of clinical concern to the dermatologist or other qualified site staff).
- Optional skin biopsy for exploratory pharmacodynamics analysis.
- In-clinic sunlight exposure test: Perform a formalized collection of the subject's time to onset of 1st prodromal symptom in sun-exposed setting (e.g. preferably outside or by window) using timer.
- AE and concomitant medication recording.
- Fitzpatrick skin type assessment.

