**Table 5 Analysis Visit Windows for the non-diary data**

Analysis visit	Nominal day	Window
Screening	Day -14	By Day -14
Day 1	First dose day	NA
Week 1	Day 8	Day 3 to 11
Week 2	Day 15	Day 12 to 22
Week 4	Day 29	Day 23 to 42
Week 8	Day 57	Day 43 to 71
Week 12	Day 85	Day 72 to 99
Week 16	Day 113	Day 100 to 134
Week 22 (FU)	Day 155	NA
End of treatment (EOT)	Week 16 study visit or study early termination visit	

The analysis visits are derived according to the following criteria:

- The unscheduled visits are not used for the deriving.
- If a study visit is the only one in an analysis visit window, this study visit becomes the derived analysis visit.
- If there are multiple visits in an analysis visit window, the closest visit to the nominal day becomes the analysis visit. In the event that two visits are the closest visits to the nominal day and equally distanced to the nominal day, the visit after the nominal day becomes the derived visit.
- The follow-up visit will not be derived. The study visit will be used.

- Unscheduled visits and retests (same visit number assigned), will not be displayed in by-visit summary tables, but will be included in the data listings.
- The deriving analysis visit is not applicable to the data not depending on study visit, for example, the AE data.

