### 7.12.4 ECGs

ECG parameter values and changes from baseline will be summarized descriptively by treatment and analysis visit.

For ECGs, number and percentage of subjects meeting the criteria listed below will be presented in tables:

- Baseline QTc  $< 450$  msec and  $> 500$  msec at EOT
- Baseline QTc  $< 450$  msec and  $500 \text{ msec} \geq \text{QTc} > 480$  msec at EOT
- Baseline QTc  $< 450$  msec and  $480 \text{ msec} \geq \text{QTc} > 450$  msec at EOT
- Change from baseline at EOT in QTc  $> 30$  msec
- Change from baseline at EOT in QTc  $> 60$  msec

These criteria will be applied to both QTcB and QTcF.

Shift tables will present the changes in clinically relevant categories from baseline to EOT. The categories are Normal, Abnormal-not-clinically significant and Abnormal-clinically significant.

All ECG parameters and findings will be listed.

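### The documents do not agree on what triggers the end-of-treatment visit, so an ECG taken weeks after the last dose can be tabulated as the EOT QTc result

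*Protocol*

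**What the plan says.** **Trigger for Visit 8.**
- Protocol 4.5 attaches the assessments to leaving the study: "In case of permanent discontinuation from study, the end of treatment and follow-up visit assessments should be performed, as completely as possible".
- Protocol 5.3.2.7 places the visit at Week 16 (Day 113±7) or early termination, without saying of what.
- SAP Table 5 defines the EOT analysis visit as "Week 16 study visit or study early termination visit".

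**Subjects who stop treatment.** Protocol 4.5 says that those who are "withdrawn from study treatment should be encouraged to complete all study visits and study procedures as outlined in the protocol". It adds: "Subjects withdrawn from treatment may remain on study and continue with study procedures off treatment", at the investigator's discretion. Section 4.6 also allows withdrawal from treatment while remaining on study.

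**ECG.** Protocol 2.2.4 lists "12-lead ECG at Baseline and EOT", so one scheduled post-baseline recording per subject. Section 6.9.3 asks for supine rest and sets no time from dose. In SAP 7.12.4 the QTc categories are all evaluated at EOT (for example "Change from baseline at EOT in QTc"), as is the shift table. None has a last-dose limit. SAP 5.4.4 does not use unscheduled visits to derive analysis visits.

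**The concern.** An end-of-treatment safety reading is normally understood as one taken on drug or close to the last dose. Here the label follows the visit and not the dose. A subject can stop drug early, follow the encouragement to stay, and reach Visit 8 at Week 16 with no drug left. Nothing in the SAP separates that ECG from one taken on drug.

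If a site does record an ECG when treatment stops, it belongs to an unscheduled visit or to a visit with no planned ECG. It would not become the EOT value.

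The QTc categories and the shift table each rest on this one scheduled recording, in arms of 34. Off-drug readings pull mean changes toward zero and lower the expected counts in the QTc categories, so the error favours the drug.

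**Working it through.** The plan gives no figure for ECG timing, so there is none to reproduce. The check compares the sections and then does day arithmetic.

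**Inputs.** Visit 8 at Day 113±7, that is Day 106 to 120 (Protocol 5.3.2.7). Mean half-life on Day 14 of 10.56 to 18.97 h, in the healthy-subject Phase I study (Protocol 1.5). 34 subjects per arm (Protocol 4.1).

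**1. The two readings of early termination.**
- *Of the study.* A subject who stops drug and stays has Visit 8 at Week 16, off drug.
- *Of treatment.* Visit 8 moves to the stop, and follow-up comes 6 weeks later (Protocol 5.3.3). For anyone stopping before Week 16 − 6 = Week 10, follow-up falls before Week 16. A Day 29 stop gives Day 29 + 42 = Day 71, against Day 113. That does not fit the request in 4.5 to complete all visits.

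Neither reading agrees with every section.

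**2. Gap from last dose to ECG under the first reading.** Gap = ECG day − last-dose day.

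| Last dose | Gap (days) |
|---|---|
| Day 8 | 98 to 112 |
| Day 15 | 91 to 105 |
| Day 29 | 106 − 29 = 77 to 120 − 29 = 91 |
| Day 57 | 49 to 63 |

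**3. Washout.** 5 × 10.56 h = 52.8 h = 2.2 days; 5 × 18.97 h = 94.9 h = 4.0 days. With first-order decay (assumed), the fraction of peak left is 2^(−t/half-life). At 7 days and the longer half-life, 2^(−168/18.97) = 0.22%. Every gap in step 2 is far beyond this.

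**4. Dilution.** If k of 34 subjects in an arm are off drug at EOT and carry no effect, the mean effect shrinks by k/34. The documents give no value for k. For illustration, 5% to 20% of 34 is about 2 to 7 subjects: 2/34 = 6% and 7/34 = 21%. An assumed true effect of 10 msec would appear as 9.4 to 7.9 msec.

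**5. Timing within the dosing day, for subjects still on drug.** Protocol 1.5 gives median tmax "values ranging from 4 to 5 hours post-dose on both Day 1 and Day 14". A one-compartment steady-state model (assumed; 24 h interval, absorption rate solved for tmax 4 or 5 h) gives these concentrations as a share of peak:

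| Time after dose | Share of peak |
|---|---|
| Just before the next dose | 31–55% |
| 1 h | 65–79% |
| 2 h | 83–93% |
| 3 h | 94–99% |
| 4 to 10 h | 76–100% |

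Only an ECG taken before the dose or within about the first hour is well below peak. The documents do not say when in the visit it is taken.

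**The case against.** **The trigger is ambiguous, not plainly wrong.** Visit 8 is titled the end-of-treatment visit. Protocol 3.2 places follow-up six weeks after the end of treatment or early termination, and section 8 counts it from the last treatment visit. SAP 5.4.10 ends treatment exposure at the EOT visit date, so the SAP treats that visit as the end of dosing. In Table 5, *study visit* contrasts with *analysis visit*, so the early-termination wording there may mean only the visit actually attended. This stands: a reader might infer that the plan definitely triggers EOT on leaving the study, and the documents do not settle it. But ambiguity is itself the defect. Under 5.4.10 the Day 29 stopper seen on Day 113 would be credited with 113 − 1 + 1 = 113 days of exposure.

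**Adverse-event stoppers need not be affected.** Protocol 4.5 lists intolerable adverse events under withdrawal from the study, which does trigger the EOT assessments. This stands: it cannot be said that all such subjects contribute an off-drug ECG. Some may, since 4.5 allows and encourages staying.

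**There is other ECG information.** All ECG parameters are summarised and listed, clinically significant abnormalities become adverse events, and unscheduled assessments are allowed. So the QTc categories are not the trial's only ECG safety result. These sources do not repair the EOT tables.

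**It could be handled later.** Withdrawal dates are recorded, dose times are recorded with PK samples, and the blinded data review may add rules. That shows the repair is feasible, not that it is planned.

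**No cardiac signal is visible.** This is true of the readable text. Safety pharmacology is blacked out, so the need for peak-timed ECGs cannot be judged either way.

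**Conclusion.** The point holds as a conflict over the trigger plus a missing last-dose rule in the SAP. As the SAP can be applied, an ECG 77 to 91 days after a Day 29 stop enters the EOT QTc categories and shift table as if on drug, and biases any effect toward zero. The washout figures assume that Phase I half-lives carry over to EPP and that decay is first-order; the gaps are so long that neither assumption is critical. The 6% to 21% dilution rests wholly on an assumed count. Completers are on or near drug at Week 16 and are not affected.

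Three stronger inferences are not supported:
- *That a concentration-related QTc effect is understated by 21% to 35% in general.* That is the shortfall at exactly 1 h after the dose (100 − 79 to 100 − 65). At 2 h it is 7% to 17%, and no section says the ECG is done on arrival.
- *That melanin is mislabelled in the same way.* It is analysed at Weeks 8, 16 and 22, not as EOT. Nevi are also assessed at Week 8.
- *That laboratory safety has the same gap.* Laboratory tests are done at every clinic visit, with liver markers also at Weeks 1 and 2.

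**What to change.** 1. **Protocol 4.5, 5.3.2.7, 5.3.3 and SAP Table 5.** State whether early termination means of treatment or of study, and make the sections agree. For subjects who stop treatment but stay, take the already planned Visit 8 ECG at the visit where permanent stopping is recorded. Leave the Week 16 melanin, nevi, laboratory and diary assessments on schedule. This concerns when a measurement is taken; no rule on dosing or on stopping treatment is proposed.
2. **SAP Table 5 and 7.12.4.** Derive on-treatment EOT from the last-dose date. Base the QTc categories and shift table on ECGs within about 4 days (five half-lives) of the last dose, allow an ECG taken at treatment stop to be used, and list off-drug ECGs separately. Four days is an outer limit: at the longer half-life about 3% of peak remains by then. It removes ECGs that cannot reflect exposure but does not guarantee exposure in the rest.
3. **Optional.** Record ECG clock time and time since last dose, and take the Visit 8 ECG next to one of the two post-dose PK samples, so that it is paired with a measured concentration. This need not fall at tmax: if the first sample is at 4 to 5 h, the second, 3 to 4 h later, is at 7 to 9 h.

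**Cost.** A few lines in each document, and an ECG moved for early stoppers. Some of them may not reach the clinic in time and will have no on-drug EOT ECG, so the QTc denominator will be slightly smaller. That is the true position.

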4.6 Study-stopping Criteria

The study may be terminated by the Sponsor at any time upon becoming aware of data that could compromise the safety and/or well-being of subjects, or for any other reason it deems appropriate. Subjects may be withdrawn from treatment and remain on study.

4.7 Lifestyle Restrictions

Subjects must adhere to the following restrictions:

1. Follow study attendance guidelines.
2. Follow study physical activity and sun exposure guidelines.
3. Female subjects of child-bearing potential or male subjects with partners of child-bearing potential must use birth control from the screening visit (for female subjects) or the first dose of study medication (for male subjects) until 3 months after the last dose of study medication.
4. 
5. Subjects must not take any prescribed or non-prescribed systemic or topical treatment (including sunscreen containing zinc oxide, herbal remedies or supplements) with known potential to have an effect on phototoxicity, photosensitivity in EPP, and/or increased pigmentation during the study. Such treatment includes, but not limited to afamelanotide, cimetidine, beta-carotene, cysteine, pyridoxine, cholestyramine, and chronic treatment with centrally acting analgesic agents (including opioids and opioid derivatives).

These restrictions are described in more detail in the following sections, and in Section

14.1, a complete list of prohibited concomitant medications is provided.

4.7.1 Subject Contraception

Female subjects of child-bearing potential and male subjects with partners of child bearing potential must be willing and able to use a highly effective method of birth control (i.e., contraceptive measure with a failure rate of <1% per year), in conjunction with male barrier contraception (i.e., male condom with spermicide) for the duration of the study, from the Screening visit until 3 months after the last dose of study medication. Male subjects must be willing and able to practice birth control for the duration of the study, from the time of the first dose of study medication until 3 months after the last dose of study medication.

Highly effective methods of contraception include:

1. Placement of an intrauterine device or intrauterine system in women.
2. Established use of oral, injected, or implanted hormonal methods of contraception associated with inhibition of ovulation.
3. Male sterilization (with the appropriate post-vasectomy documentation of the absence of sperm in the ejaculate). (For female subjects on the study, the vasectomized male partner should be the sole partner for that subject.)
4. Bilateral tubal ligation.
5. True abstinence: when this is in line with the preferred and usual lifestyle of the subject. (Periodic abstinence [e.g., calendar, ovulation, symptothermal, post-ovulation methods] and withdrawal are not acceptable methods of contraception).
6. Male subjects with partners of child-bearing potential must use a barrier method of contraception (i.e., male condom with spermicide) in addition to a second method of acceptable contraception used by their female partners. In addition to the list of highly effective contraception methods above, other acceptable second methods of female partner contraception include:
 - a. Progesterone only oral contraception, where inhibition of ovulation is not the primary mode of action.
 - b. Cap, diaphragm, or sponge with spermicide.
 - c. Male subjects must not donate sperm for the duration of the study, from the time of the first dose of study medication until 3 months after the last dose of study medication.

Women are considered to be of child-bearing potential unless they meet one or more of the following criteria as documented by the Investigator:

1. Post-menopausal for at least 1 year, confirmed by follicle stimulating hormone (FSH) assessment (>40 mIU/mL).
2. Documented hysterectomy, bilateral oophorectomy, or bilateral salpingectomy.
3. Congenital sterility.

Mitsubishi Tanabe Pharma Development America, Inc.

Subjects must not have unprotected sexual intercourse with a female who is pregnant or breastfeeding during the study.

4.7.2 Physical Activity and Subject Sun Exposure

Subjects will be encouraged to go outside during daylight hours (e.g., between 1 hour post sunrise and 1 hour pre-sunset) during the treatment period by the investigators or designated study site staff. Time outside should be correlated with or limited by the onset of prodromal symptoms. Subjects will be asked to make note of time period spent outside or until the onset of prodromal symptoms in the sunlight exposure diary. Outside exposure is considered locations outside of a building such as the time riding in a car or train. Time next to a window indoors is not considered outside exposure.

Patients will be informed by the investigator regarding the objectives of the study and the importance of the patient seeking some level of direct sun exposure on a daily basis. This discussion will include clarification that the goal is not to intentionally induce phototoxic reactions, but for the subject to spend enough time to generate some level of prodromal symptoms. The goal of the study is to determine whether the study drug has an effect on increasing the symptom-free time in the sun and/or reducing the duration or intensity of symptoms associated with sun exposure. Once randomized, no subject will be coerced into direct sun exposure that would induce phototoxicity, or discontinued for noncompliance if the subject expresses a concern for their own safety and well-being.

